5. We choose the home nearest to the sampled point.
6. On the same side of the street as that first home, demarcate a total of 6 additional homes that are evenly between the first selected home and either end of the street.
7. Randomly order these 6 additional homes and select the first three.
8. If a home includes more than one household, we number them and then draw one number at random from a hat.
9. If a household either does not consent to participation in an initial intake, is ineligible (see below), or does not consent to participate in the full study, then move to the next household in the list of 6. If one exhausts this list, then perform the same enumeration strategy on the other side of the street.

Upon being selected, an enumerator approach the household head or adult representing the household for their consent for a brief intake survey to determine the household's eligibility. Households will be eligible if it contains at least one adult member who was eligible for COVID vaccination but has never been vaccinated against COVID-19.

If eligible, the household head or adult representing the household will be asked for their consent to participate in the full study, which would involve being approached at a future date for in person "discussions of health-related issues, including adult vaccination." This consent process will be done for households in both treated and control clusters. For those in treated clusters, such "discussion" would include the visit from the health ambassador and then the endline survey. In control clusters, such "discussion" would include only the endline survey.

Recruitment and Mobilization of Health Ambassadors

Profile

The intervention aims to mobilize Health Ambassadors who meet the following criteria:

- Willing to work on a volunteer basis, exhibiting intrinsic motivation to contribute to social welfare and a willingness to engage households in an empathetic manner;
- Up to date on vaccination for COVID and other target diseases;
- Possess enough education and capacity to be a “voice for science”, that is, to effectively and accurately communicate the scientific processes and regulations that ensure vaccine safety, the scientifically understood protective benefits of vaccines, and the scientifically understood risks of vaccinations; and
- Possess connections to the communities in which target households reside so as to operate on the basis of trust.

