- Status with regard to vaccination for COVID and other target diseases;
- Education level and relevant technical experience; and
- Location of origin, current location, and languages spoken.

Incentives

The Health Ambassadors receive a small stipend to cover basic costs such as transportation, communication, and meal allowances during the days of their work. After the intervention work is completed, the research team will offer to them the opportunity to participate in a training activity on the research, which will include a mix of in-person and Zoom sessions with the broader international research team. We will also organize the opportunity for them to meet with leadership from the Ministry of Health to commend their contributions. The Health Ambassadors will also receive certificates of participation endorsed by the organizing institutions.

This incentive strategy assumes that those with strong intrinsic motivation will be best positioned to strike trusting relationships with the participant households. The opportunities for training will further enhance this selection based on intrinsic motivation.

Numbers and Timeline

16 Health Ambassadors are mobilized per country, with each Health Ambassador covering one treated cluster. They will have 6 weeks to work with the 24 households in their cluster. However, in Senegal, due to personal constraints, one health ambassador was unable to start the work just before the intervention and was replaced by another. This maintained the total number of health ambassadors in Senegal at 15. They are required to have one initial engagement and then at least one follow-up engagement with each of the 24 households (although additional engagements are encouraged). Individual engagements should consist of a conversation with the head of household and other adult, on a one-on-one basis and in private. Each conversation is expected to last 30 minutes. However, in some cases, the conversation may extend beyond the designated 30-minute timeframe if all parties have an interest to do so.

Health Ambassador Assignment to Households

In Malawi and Zimbabwe, Health Ambassadors are health workers who already have designated communities. They will continue to work in those communities, although they will be employing novel techniques for engaging households relative to current approaches.

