In Cote d'Ivoire and Senegal, Health Ambassadors are assigned to the treatment clusters, conditional on meeting the language and "connection to community" requirements.

Health Ambassadors Protocol for Discussions with Households

Health Ambassadors are trained using a handbook that defines the protocol for engaging household members. The handbook contains the following elements:

- Relevant *scientific information* on vaccine safety, the scientifically understood protective benefits of vaccines, and the scientifically understood risks of vaccinations, along with a brief “factsheet” to use as a tool when engaging households. This scientific information is drawn from factsheets and other outreach materials produced by the health ministries from each of the study countries.
- Guidance material on the strategy for engaging in conversations with households. The engagement strategy is based on the AIMS (Announce, Inquire, Mirror, Secure) methodology as explained in Parrish-Sprowl et al. (2023). The AIMS approach was designed specifically to address mistrust in the scientific and medical establishments that drives vaccine hesitancy. The assumption is that overcoming such mistrust requires meaningful interactions, and cannot be addressed by unilateral messaging alone. Moreover, the interactions need to be carried out in a way that is effective for building trust. Thus, health workers, who represent the scientific and medical establishments, will employ active listening so as to engage households in a manner that is empathetic and seeking to learn household members’ points of view, while also trying to persuade them of the value of vaccination and of using “critical thinking” to scrutinize information about vaccination received from non-science-based sources. The health workers will be trained to avoid any confrontation or disparagement of household members’ points of view, as this can undermine the goal of building trust.

We also hope to offer households an embodiment of a trustworthy “voice for science” in the minds of households, while conveying skills for scrutinizing health information.

Health Ambassadors Training

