- Co-ethnicity with respondent,
- Personality measure of empathy (empathy assessment scale).

This analysis will take advantage of the random assignment of health ambassadors to households. We will perform a “dummy” random assignment for the control group so that we know, for each control group household, which of the health ambassadors *would* have treated them, counterfactually.

These analyses will be conducted as separate one-way interaction regressions with the following specifications:

$$y_{vji} = \alpha + \beta_1 Treated_i + \beta_2 W_{ji} + \beta_3 Treated_i * W_{ji} + Vaccine FE_v + Rand. Block FE_{b[i]} + X_{ji}'\gamma + \epsilon_{vji} , \quad (4)$$

$$y_i = \alpha + \beta_1 Treated_i + \beta_2 W_i + \beta_3 Treated_i * W_i + Rand. Block FE_{b[i]} + X_i'\gamma + \epsilon_i , \quad (5)$$

where W_{ji} or W_i refers to the background characteristic in question. We will use FDR control on the p-values for the respondent attribute (as one family of estimates) and then the health ambassador attributes (as a separate family) interaction effect estimates.

Mechanisms through which the intervention may increase vaccine uptake

To identify the mechanisms through which the intervention may increase the primary outcome of interest, we estimate the following two equations:

$$M_{ji} = \alpha^M + \beta^M Treated_i + Rand. Block FE_{b[i]} + X_{ji}'\gamma^M + \epsilon_{vji}^M \quad (6)$$

$$Y_{ji} = \alpha^Y + \beta^Y Treated_i + \kappa M_{vji} + Rand. Block FE_{b[i]} + X_{ji}'\gamma^Y + \epsilon_{vji}^Y \quad (7)$$

The “first stage” effect of the Health Ambassador treatment on the mediating variables is captured by β^M and then the extent to which a mediating variable is responsible for transmitting the effect of the HA treatment onto vaccine outcomes is given by $\beta^M \kappa$. We will use the Imai et al. “mediation” software in R to implement this analysis. We hypothesize that the intervention will improve vaccine trust through subjects' acceptance of the benefits of vaccination, subjects' access to vaccination and affordability. Additionally, the subjects are aware of the availability of vaccines and the benefits and risks associated with the vaccine and are motivated to seek vaccination. Moreover, the subjects accept the medical system as a trustworthy healthcare provider.

Descriptive Analyses of Process and Context

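### The exploratory ambassador-attribute analysis claims a random assignment of ambassadors that the protocol does not describe, so its interaction estimates are not protected from confounding by community

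*Protocol*

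**What the plan says.** The protocol section Effect Heterogeneity with Household Data proposes an exploratory analysis of moderators in two families: respondent attributes and ambassador attributes (gender, age, degree programme, co-ethnicity, empathy). For the second family it states: "This analysis will take advantage of the random assignment of health ambassadors to households". It then adds a dummy "random assignment for the control group so that we know, for each control group household, which of the health ambassadors" would have visited it. Models (4) and (5) regress the outcome on treatment, the attribute W, their product, block effects and covariates. The coefficient of interest is beta3, on the product.

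Other sections describe how ambassadors are placed:

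- Cluster Randomization randomises clusters to treatment or control, stratified by city and, where possible, health district. It randomises nothing else.
- Numbers and Timeline has 16 ambassadors per country, "with each Health Ambassador covering one treated cluster". It later gives 15 for Senegal.
- Health Ambassador Assignment to Households: "In Malawi and Zimbabwe, Health Ambassadors are health workers who already have designated communities", and they go on working there. For Côte d'Ivoire and Senegal, "Health Ambassadors are assigned to the treatment clusters, conditional on meeting the language" requirement and a second one of connection to the community.
- Profile lists as a criterion: "Possess connections to the communities in which target households reside so as to operate on the basis of trust". Recruitment also aims at people from the region where they will work.

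**The concern.** The ambassador interactions would support a statement about which kind of ambassador works better only if attributes were allocated independently of the communities served. The protocol claims that property but describes a different process. With one ambassador per treated cluster, gender, age, degree and empathy are constant within the cluster and tied to that community. Co-ethnicity can vary between households but depends on the same placement.

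The dummy draw does not restore comparability. In treated clusters W belongs to someone placed there by prior posting or by eligibility. In controls W comes from a lottery and cannot be related to the household's community. A community trait that goes with both the attribute and the outcome level therefore acts in one arm only and appears as effect modification. Block effects do not remove differences between clusters in the same block, and FDR control limits chance findings but not bias. At stake is whether a set of exploratory moderators is published as randomised evidence.

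**Working it through.** **1. Textual check.** The contradiction needs no arithmetic. The claim is random assignment of ambassadors to households. For Malawi and Zimbabwe the assignment section says the opposite. For Côte d'Ivoire and Senegal it gives a conditional rule at cluster level. A random draw among eligible ambassadors would fit that rule, but it is not stated and would still not be at household level.

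**2. The plan's own figures.** The section Cluster selection gives (16 + 16) × 4 = 128 clusters and (16 + 16) × 24 × 4 = 3,072 households, and both reproduce. It gives no ICC, so its 80% power cannot be reproduced directly. A 0.15 SD difference needs 698 households per arm without clustering (two-sided 5%, 80% power). The plan has 1,536, so it tolerates a design effect of 1,536/698 = 2.20, or an ICC of (2.20 − 1)/23 = 0.052. An ICC of 0.05 is therefore a reasonable assumption for illustration.

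**3. Expected bias in beta3.** Assume that W is binary with prevalence one half and that its latent score has correlation rho with the cluster's outcome level. Assume also that controls get a random W and that there is no true modification. The treated-arm slope on W is 2 × √(2/π) × rho × √ICC = 1.596 × rho × √ICC, and the control slope is zero, so this is the bias. At ICC 0.05 (√ICC = 0.2236):

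- rho 0.3: 1.596 × 0.3 × 0.2236 = 0.107 SD
- rho 0.5: 1.596 × 0.5 × 0.2236 = 0.178 SD

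**4. Expected false-positive rate.** The variance of a cluster mean is 0.05 + 0.95/24 = 0.0896. With four cells of about 32 clusters, the SE of beta3 is √(4 × 0.0896/32) = 0.106. The shift is 0.107/0.106 = 1.01 at rho 0.3 and 0.178/0.106 = 1.68 at rho 0.5. The chance of exceeding 1.96 is then about 17% and 39%.

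**5. Simulation of model (5).** It was run on cluster means with 128 clusters of 24, 8 blocks (assumed) with block effects, robust SEs, a binary W, true beta3 = 0 and 1,500 runs. Controls received a dummy drawn at cluster level within block. Entries are mean beta3 in SD and rejection rate.

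| ICC | rho 0 | rho 0.3 | rho 0.5 |
|---|---|---|---|
| 0.02 | 0.001; 5.5% | 0.069; 13.1% | 0.115; 26.2% |
| 0.05 | −0.004; 5.5% | 0.104; 16.4% | 0.180; 39.5% |
| 0.10 | 0.004; 5.7% | 0.146; 20.8% | 0.249; 50.0% |

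This agrees with steps 3 and 4. When the same matching rule is used in both arms, mean beta3 stays within 0.006 of zero and rejection between 4.3% and 6.1%. Under true random assignment in both arms, the figures are 0.004 and 4.1% to 5.9%.

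**6. Sensitivity to the covariates.** The simulation in step 5 has no X. The protocol's covariates include the cluster's pre-intervention vaccination rate. If X explains half of the cluster variance (assumed), rejection for a binary W at ICC 0.05 falls to about 9% to 10% at rho 0.3 and 19% to 23% at rho 0.5.

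**The case against.** The strongest reply is that little depends on this. The section is labelled exploratory, and the claim concerns one family of five attributes. The vaccine-trust effect, the vaccination effect and the respondent-attribute interactions do not use the assignment of ambassadors. That stands, and it limits the severity.

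Several stronger readings are tempting but are not supported:

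- A reader might infer that ambassadors were shown not to be randomised in all four countries. The contradiction is outright in two. In the other two the documents state no random draw but do not exclude one among eligible ambassadors.
- A reader might infer that the estimates are confounded and will yield spurious moderators. Bias requires the attribute to be correlated with the cluster's outcome level, and the documents say nothing about that correlation.
- A reader might infer that co-ethnicity is raised by selection, or that degree type is simply a country contrast. Ethnicity is not a selection criterion, although language and connection may favour it. Several degree fields occur within Côte d'Ivoire and Senegal. What remains is that ambassador type differs by country and models (4) and (5) have no treatment-by-country term, so country differences in effect could leak into the degree interaction.
- A reader might infer that these results will decide whom ministries recruit. The stated objectives are impact, mechanisms and cost-effectiveness at scale.

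The exploratory label does not answer the core point. It lowers the weight of the results but does not make an incorrect statement about the design correct.

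**Conclusion.** The point holds in a limited form. The random-assignment claim is contradicted for Malawi and Zimbabwe and unsupported for Côte d'Ivoire and Senegal, and the random dummy does not supply a comparable control value of W. Beta3 for the ambassador attributes is therefore not protected from confounding by community.

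How large the bias is cannot be learned from the documents. Over assumed ICCs of 0.02 to 0.10 and assumed correlations of 0.3 to 0.5, it is 0.07 to 0.25 SD, with false-positive rates of 13% to 50% before covariates. The middle case, about 0.10 to 0.18 SD, is of the same order as the 0.15 SD effect the trial is powered for. With zero correlation there is no bias and the error rate is nominal. The main conclusions of the trial do not depend on this analysis.

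**What to change.** 1. Delete the random-assignment sentence and state the actual rule for each pair of countries.
2. Build the control-arm dummy at cluster level with that same rule, wherever data already held allow it. In Côte d'Ivoire and Senegal this means the language and connection eligibility. In Malawi and Zimbabwe it means the worker designated to the control cluster, but only if that worker's attributes are available: the protocol describes collecting such information from candidate ambassadors only.
3. Where the rule cannot be reproduced, fit the attribute model in treated clusters only, with block effects and covariates. This estimates the treated-arm association and should be labelled as that.
4. Report all ambassador-attribute results as exploratory, non-randomised associations based on at most 64 ambassadors (16 × 4; 63 if Senegal had 15). Keep the FDR families.

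The cost is a change of wording and a new dummy rule, with no new household data. The downside is that these results can no longer be presented as a randomised comparison. Even with the same rule in both arms, a difference in effect by attribute may reflect the community rather than the ambassador.

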We select a common number of clusters within each of the four study countries. The goal is to have enough clusters so that the study is powered to detect a 0.15 control group standard deviation effect (Glass’s Delta) on the Vaccine Trust Indicator (VTI), equivalent to a 7ppt. effect on the vaccination rate outcome, with 80% power and 95% confidence in an analysis that pools that data from the four countries. For the power analysis for the VTI (our primary outcome variable), we assume the control group VTI outcomes are normally distributed (we use this assumption due to the unavailability of actual distributional information on the VTI for the countries under investigation at the time of power calculation) and that all outcomes are normalized relative to the control group standard deviation. For vaccination rates, we used the most recently available (as of summer 2023) health-district-level COVID-19 vaccination rates (when available) as the input data. We simulated a 0.15 control group SD effect, which was equivalent to a 7 ppt. effect on vaccination, and then evaluated what sample size would be needed to achieve 80% power with 95% confidence. The power analysis showed that having **16 treated clusters and 16 control clusters per country and 24 households per cluster** would suffice. This implies $(16+16)*24 = 768$ **households sampled per country**, with an **overall sample size of 3,072 households and 128 clusters** across all four countries.

The study aims to increase vaccine trust, with COVID-19 vaccination being the primary basis for assessing current hesitancy. In each country, our primary focus lies on the two largest, most densely populated cities. This strategic decision is driven by the critical need for vaccination in these regions, owing to their heightened potential for disease transmission and the prevailing low COVID-19

vaccination rates. In each priority locality, clusters are defined as neighbourhoods served by health centers or clinics that meet the following criteria:

- The health center must offer COVID-19 vaccination services and services for other target vaccines (varies by country).
- For each targeted city, the health facilities used for defining the clusters must be separated by a distance of at least 4 to 5 km. This precautionary measure is taken to prevent potential spillover effects.

We proceed by describing the criteria employed for selecting priority districts within each country.

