Please give your level of agreement with each statement using the scales provided (where 1 = strongly disagree/strongly against vaccination and 10 = strongly agree/strongly in favor of vaccination).

- 1.1. Thinking about vaccination in general, would you say you are...
1=strongly against vaccination, 10=strongly in favour of vaccination
- 1.2. I generally trust vaccine manufacturers or pharmaceutical companies
1=strongly disagree, 10=strongly agree
- 1.3. I generally trust the {country specific health department}
1=strongly disagree, 10=strongly agree
- 1.4. I understand how vaccination helps my body fight infectious disease
1=strongly disagree, 10=strongly agree
- 1.5. I feel it is important that I get vaccinated
1=strongly disagree, 10=strongly agree
- 1.6. Vaccination forms part of a healthy lifestyle
1=strongly disagree, 10=strongly agree

The items are summed to create a composite vaccine trust score. We will standardize in terms of control group standard deviations.

Secondary outcome measures

These secondary outcomes will be measured through a household questionnaire at baseline (before the intervention) and endline (after the intervention). The following questions will be asked to adult members of the household.

1. Vaccine uptake

- 1.1 For each vaccine and each target household members, the individual questionnaire will indicate whether the respondent (i) did not verbally affirm receiving the vaccination or provide documentation, (ii) verbally affirmed vaccination but did not provide documentation, or (iii) provided documentation of vaccination.

For respondents who have not been vaccinated due to time constraints or limited access to health centers, the survey will capture their intention to receive the vaccine if they were at a health center using the following question: Are you planning to be vaccinated for the [country specific disease] vaccine?

2. Knowledge about the disease: I will read you some statements and I would like you to tell me how much you agree or disagree with each statement. Please say whether you strongly agree, agree, neither agree nor disagree, disagree, or strongly disagree.
 - 2.1. [The targeted disease name] exists.
 - 2.2. I am aware of how [The targeted disease name] is transmitted.
3. To the best of my knowledge, [Targeted disease name from the list] require vaccines for their cure?
4. Vaccine/disease knowledge:

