- For the global index, we will use the standard asymptotic p value and a two-sided null hypothesis with 95% confidence.
- If the global p-value rejects the null, then for the grouping-specific indices, we will use a Benjamini-Hochberg FDR correction for the 4 p-values.
- For any grouping index that rejects the null, we will use the Benjamini-Hochberg FDR correction for the item level p-values.

For estimating peer effects, we will use the same specification (2), with l indexing the peer respondent and $Treated_i$ indicating the treatment status of the person that recommended them.

For our behavioral outcome measured in the household roster, we will estimate the average treatment effect on the pooled vaccination rate using the following regression specification:

$$y_{vji} = \alpha + \beta Treated_i + Vaccine FE_v + Rand. Block FE_{b[i]} + X_{ji}'\gamma + \epsilon_{vji} , \quad (2)$$

where v indexes the vaccine, j indexes the individual adult in the household roster, i indexes the household, and $b[i]$ indexes the randomization block for household i . The variable $Treated_i$ is an indicator for whether the household is in a treated cluster or not. Then, $Vaccine FE_v$ are fixed effects (dummy variables) for the different vaccines and $Rand. Block FE_{b[i]}$ are fixed effects (dummy variables) for the randomization blocks. The covariate vector X_{ji} includes the following elements:

- Indicator for female of individual j ,
- Age for individual j ,
- Level of education for individual j ,
- Pre-intervention vaccination rate in the household's cluster.

We calculate cluster-robust standard errors taking the error term ϵ_{vji} to be clustered at the level of the randomization cluster. We hypothesize that $\beta > 0$, and we test using a two-sided test (allowing for the possibility that effects could go in the opposite direction as what is hypothesized) with 95% confidence. If we reject the null, we will then test effect on each individual vaccine, using the Benjamini-Hochberg FDR correction for the vaccine-level p-values.

Effect Heterogeneity with Household Data

We propose an exploratory analysis of background conditions that may moderate the size of the treatment effects on behavior and attitudes. These include:

Respondent attributes:

- Gender,
- Age,
- Level of education,
- Ethnic group (coded for collectivist norms),
- Proximity to health center.

Health ambassador attributes:

- Gender,
- Age,
- Type of degree program,

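### The mediation analysis does not fix its outcome; if that outcome is vaccine trust, several named mediators overlap VTI items and κ cannot be read as a mechanism

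*Protocol*

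**What the plan says.** Three statements in the same section of the protocol's Analysis Plan bear on the mediation outcome.

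- The heading reads "Mechanisms through which the intervention may increase vaccine uptake".
- The opening sentence sets out to identify "the mechanisms through which the intervention may increase the primary outcome of interest". The section on the primary outcome measure defines that outcome as vaccine trust, measured by the VTI.
- The hypothesis begins "We hypothesize that the intervention will improve vaccine trust through" and goes on to name the pathways: acceptance of the benefits, access, affordability, awareness of availability, awareness of benefits and risks, motivation to seek vaccination, and acceptance of the medical system as trustworthy.

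Equation (6) regresses the mediator on treatment (β^M). Equation (7) regresses the outcome on treatment and mediator (κ). The product β^M × κ is read as how far the mediator transmits the treatment effect.

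The VTI is a sum of six items. Item 1.3 is "I generally trust the {country specific health department" and item 1.5 is "I feel it is important that I get vaccinated". Item 1.4 asks about understanding how vaccination works, and item 1.6 about vaccination as part of healthy living.

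**The concern.** A mediation analysis has to state what is being explained. Here the heading points to behaviour and the text to an attitude score, and the two choices have different validity problems.

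On the trust reading, part of the mediator list describes the outcome in other words. Two survey answers given by one person on one occasion about nearly the same thing will correlate, whether or not one causes the other. Only treatment is randomised, so nothing in the design separates that correlation from a causal step.

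Understanding mechanisms is the second of the protocol's three objectives. A sizeable mediated share produced by shared content would be reported as the way the intervention works, and could steer how it is scaled up.

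**Working it through.** **1. Which outcome do the equations use?**

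| Equation | Outcome | Mediator | Covariates | Error | Vaccine fixed effects |
|---|---|---|---|---|---|
| (1) attitudes | y_i | none | X_i | ε_i | no |
| (2) uptake | y_vji | none | X_ji | ε_vji | yes |
| (6) | none | M_ji | X_ji | ε_vji | no |
| (7) | Y_ji | M_vji | X_ji | ε_vji | no |

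The subscript j (roster adult) suggests uptake. The missing vaccine index on Y and the missing vaccine fixed effects do not fit equation (2). The mediator itself is M_ji in (6) and M_vji in (7). The notation does not settle the matter.

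**2. Which mediators overlap the VTI?**

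| Mediator | Nearest VTI item |
|---|---|
| Acceptance of benefits | 1.5, 1.6 |
| Motivation to seek vaccination | 1.5 |
| Medical system trustworthy | 1.3 |
| Awareness of benefits and risks | 1.4, in part |
| Access, affordability, awareness of availability | none |

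The protocol describes mediators in words and does not tie them to items. That they come from the same endline interview is inferred from the matching questions being in the same household questionnaire.

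**3. Do the covariates help?** The list under equation (2) is sex, age, education and the cluster's pre-intervention vaccination rate. It has no baseline mediator, although the secondary measures are taken at baseline and endline.

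**4. Share produced by overlap alone.** Assume that treatment shifts one common attitude, that every item moves by d, that items have unit variance and correlation r, and that no item causes another. Let M be a parallel item outside the VTI and S the sum of the six VTI items.

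- β^M = d
- κ = Cov(M, S)/Var(M) = 6r
- total effect on S = 6d
- share = (d × 6r)/(6d) = r

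Standardising S cancels. The share is 20%, 40% and 60% at r = 0.2, 0.4 and 0.6. The documents give no value of r; this range is an assumption.

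**5. How often would it look significant?** The protocol gives no figure for the mediation analysis, so its overall design was used: "powered to detect a 0.15 control group standard deviation effect", "with 80% power and 95% confidence in an analysis that pools that data from the four countries". The sample reproduces as (16 + 16) × 24 = 768 and 768 × 4 = 3,072. No intracluster correlation (ICC) is stated. At an assumed 0.05 the design effect is 1 + 23 × 0.05 = 2.15. With 698 per arm before clustering, 2 × 698 × 2.15 ≈ 3,001, and 3,072 households give 80.9% power. The simulations use that ICC.

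Equations (6)-(7) were simulated with 128 clusters of 24, 8 assumed blocks, cluster-robust errors and 500 runs per setting. The mediator and the VTI score had residual correlation ρ and no causal path between them. In general the share is ρ × (mediator shift ÷ VTI shift, both in SDs).

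With 0.15 SD on the VTI, the runs with a 95% interval for β^M × κ above zero, and the mean share, were:

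| ρ | Mediator shift ρ × 0.15 | Mediator shift 0.15 |
|---|---|---|
| 0.3 | 18%, share 0.10 | 84%, share 0.31 |
| 0.5 | 30%, share 0.25 | 82%, share 0.49 |
| 0.7 | 56%, share 0.50 | 82%, share 0.70 |
| 0.9 | 72%, share 0.80 | 83%, share 0.91 |

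κ was significant in every run once ρ was 0.1 or more. With no treatment effect on either variable, a positive indirect effect appeared in 2.2% to 3.6% of runs. With 0.15 SD on the VTI and an unmoved mediator, it appeared in 0% to 3.8% (ρ from 0 to 0.3).

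**The case against.** The best defence is that uptake is the intended outcome. The heading says so, and the j and v subscripts belong to the behavioural equation. Attitudes are then ordinary mediators of behaviour, and the overlap disappears. This stands as a reading, but the text contradicts it twice, by naming the primary outcome and by naming vaccine trust. Even with uptake as Y, unmeasured confounding between mediator and outcome would remain.

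A second defence is that β^M is protected by randomisation. That is correct. A reader might infer from the overlap that a positive mechanism finding is close to certain. The simulations do not support that: the false-positive rate is about 2% to 4% when treatment moves nothing, and 18% to 84% at the design effect, depending on the overlap and on how far the mediator moves. Only the κ leg is near certain.

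A third is that not every mediator is a trust construct. Also correct: access, affordability and awareness of availability have no VTI counterpart.

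A reader might also suppose that a VTI item would itself serve as mediator of the VTI, which would give larger artificial shares. The protocol does not propose this, and separate items exist for beliefs, access and the healthcare system, so no such figure is used here.

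Finally, the choice of mediator items and any sensitivity analysis for unmeasured confounding may be in an SAP that is not at hand. Their absence is not counted. The contradiction over the outcome is in the protocol itself.

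**Conclusion.** The protocol contradicts itself on the outcome of equations (6)-(7). This rests on the text alone and needs no assumption.

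The second part is conditional. If Y is the VTI, κ for the benefit, motivation and medical-system mediators, and partly for awareness of benefits and risks, cannot separate a causal path from shared content. The size depends on quantities the protocol does not give: about r for a parallel item under a one-factor model, and in the simulations anywhere from 0.10 to 0.91 of the total effect, depending on ρ and the mediator shift. These are shares that could arise without any causal path. They are not a claim that the true mediated share in this trial is zero.

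The primary treatment-effect estimate is untouched. The point should be corrected because, on the trust reading, the plan could give a misleading answer to a stated objective.

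**What to change.** - Name one Y and correct the subscripts of (6)-(7), so that M carries the same index in both equations. State the level at which the mediator is measured: the individual questionnaire has one respondent per household, whereas equation (2) has one record per roster adult and vaccine.
- Preferably make Y uptake, as the heading says, with the equation (2) outcome and vaccine fixed effects, and use the attitude and access indices as mediators. Do not use as mediator an item that itself records vaccination status, such as item 7.2.
- If trust is kept as Y, exclude mediators whose content duplicates VTI items. Access, affordability and awareness of availability can stay.
- In either case add the baseline mediator to (6)-(7), and the baseline outcome where it was collected. Baseline collection is stated for the secondary measures, which include uptake; a baseline VTI is not expressly promised.
- Do not present β^M × κ as the part of the effect for which a mediator is responsible without stating that the mediator is not randomised.

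The cost is protocol or SAP wording and a few lines of code. The baseline secondary measures are already planned. The downside is that mediated effects will look smaller and less certain.
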